### 9.4.2. Immunogenicity Assessments

Samples for immunogenicity testing including a pharmacokinetic sample will be collected at Visit 2, and at later time points in case of event judged by the investigator to be a potential systemic allergic/hypersensitivity reaction, when possible. Venous blood samples (approximately 10 mL) will be collected in tubes and used to determine antibody production against ixekizumab. The actual date of each sampling will be recorded on the laboratory requisition. To analyze change from baseline, the exploratory sample collected at Visit 2 will be used. If analyzed, the samples will be evaluated in validated immunogenicity assays at an external vendor in a screening assay and if positive a neutralizing ADA assay. Assay validation details are available upon request.

Samples from patients treated with guselkumab will not be analyzed for anti-guselkumab antibodies. These samples will be discarded at the end of the study. Immunogenicity will be assessed by a validated assay designed to perform in the presence of ixekizumab. Antibodies may be further characterized and/or evaluated for their ability to neutralize the activity of ixekizumab. Samples will be retained for a maximum of 15 years after the last patient visit or for a shorter period if local regulations and ERBs allow, at a facility selected by the sponsor, to enable further analysis of immune responses to ixekizumab. This duration will allow the sponsor to respond to regulatory requests related to the study drug. Any samples remaining after 15 years will be destroyed.

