### **10.3.5. Evaluation of Immunogenicity**

For patients randomized to ixekizumab who experience a potential systemic allergic/hypersensitivity event during the study, an immunogenicity sample will be collected and evaluated for ADA compared to a stored baseline sample if possible. Immunogenicity samples will not be evaluated for anti-guselkumab antibodies.

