6.16.1.1. Sample Category Definitions

Samples are classified into the following categories:

- **Unevaluable sample:** Sample could not be tested for anti-drug antibody (ADA) due to sample loss, mishandling, or errors in collection, processing, storage, etc.
- **Antidrug antibody (ADA) Positive sample:** The presences of ADA is detected and confirmed. The samples are reported as positive. If the sample is positive, a titer value is reported.

- **Neutralizing anti-drug antibody (NAb) Positive sample:** NAb are reported as detected.
- **ADA Negative sample:** The presence of ADA is not detected and the assay drug tolerance level is not exceeded.
- **NAb Negative sample:** The presence of NAb is not detected and the assay drug tolerance level is not exceeded.

Inconclusive sample: when ADA/NAb is not detected in a sample but drug is present in the same sample at a level that can cause interference in the ADA/NAb detection method (i.e., above the limit of drug tolerance of the ADA/NAb assay). The upper limit of drug tolerance in the ADA assay is 480.5 µg/mL and the upper limit of drug tolerance in the NAb assay is 1.1 µg/mL. A negative ADA/NAb result cannot be confirmed if drug concentrations present in the testing sample is above the limit of drug tolerance of the assay, and the sample should be considered inconclusive. [Figure RHCR.6.1](#) illustrates the relationship of some of the above terms.

Abbreviation: ADA = anti-drug antibody.

Figure RHCR.6.1. Sample definitions.

[figure not shown]

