6.16.1.3. Definitions for Clinical Interpretation of Assay Results

- **Baseline:** For immunogenicity analyses, baseline is the last nonmissing observation on, or prior to, the date of the first injection of study treatment of ixekizumab (Week 0).
- **Baseline ADA positive (preexisting antibody):** ADA detected in a sample collected at baseline.
- **TE-ADA positive:** a) a patient with a ≥ 4 -fold (or 2 dilutions) increase over a positive baseline antibody titer; or b) for a negative baseline titer, a patient with an increase from the baseline to a level of $\geq 1:10$.
- **Baseline ADA-negative:** ADA is not detected in a sample collected at baseline.
- **TE-ADA inconclusive patient:** A patient without a TE-ADA positive sample and with at least 1 sample for which drug levels may interfere with the ADA assay.
- **TE-ADA negative patient:** A patient who is evaluable for TE-ADA and is not either TE-ADA positive or TE-ADA inconclusive.

Figure RHCR.6.3 illustrates the relationship of some of these terms.

Abbreviation: ADA = anti-drug antibody.

Figure RHCR.6.3. Relationship of terms for clinical interpretation of assay results for evaluable patients.

- **Incidence of TE-ADA:** Patients with TE-ADA as a proportion of the evaluable patient population during the treatment period. This excludes unevaluable patients.

[figure not shown]
All ADA positive samples will be evaluated for NAb. NAb patient status will be defined as follows:

- **NAb-positive patient:** A patient where a NAb positive result is detected for ≥ 1 TE-ADA positive samples.
- **NAb-inconclusive patient:** A patient without a NAb positive sample and with at least 1 sample for which drug levels may interfere with the NAb assay.
- **NAb-negative patient:** A patient who is evaluable for NAb and is not either NAb positive sample or NAb inconclusive.

ADA and TE-ADA titer values will be categorized as follows:

- Low Titer if titer value (LOCF) $< 1:160$;
- Moderate Titer if titer value (LOCF) $\geq 1:160$ and $< 1:1280$; and
- High Titer if titer value (LOCF) $\geq 1:1280$.

A flow chart that reflects the connection between the analytical test results and the clinical interpretation based on the definitions is shown in [Figure RHCR.6.4](#).

Abbreviation: ADA = anti-drug antibody.

Figure RHCR.6.4. Flow chart of ADA assessment with clinical interpretation of the various result possibilities.

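### The three neutralizing-antibody patient categories in SAP 6.16.1.3 draw on different samples: read literally, they call some ADA-negative patients inconclusive and leave others in no category

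*SAP*

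**What the plan says.** SAP 6.16.1.3 introduces the NAb categories with the statement "All ADA positive samples will be evaluated for NAb". Protocol 9.4.2 gives the same sequence: samples, if analysed, go through testing "in a screening assay and if positive a neutralizing ADA assay". An ADA-negative sample therefore has no NAb assay planned.

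The patient categories in SAP 6.16.1.3 are:

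- **NAb-positive:** "A patient where a NAb positive result is detected for ≥ 1 TE-ADA positive samples".
- **NAb-inconclusive:** "A patient without a NAb positive sample and with at least 1 sample for which drug levels may interfere with the NAb assay".
- **NAb-negative:** whoever is evaluable for NAb and has neither a NAb positive sample nor inconclusive status. Evaluability is defined for ADA in SAP 6.16.1.2, but not for NAb.

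SAP 6.16.1.1 sets the ADA assay's drug tolerance at 480.5 µg/mL and says that "the upper limit of drug tolerance in the NAb assay is 1.1" µg/mL. A sample is ADA negative when no ADA is found and the drug level is within the assay's tolerance.

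Post-baseline sampling is event-driven. Under Protocol 10.3.5, for ixekizumab patients with a potential systemic hypersensitivity event, "an immunogenicity sample will be collected and evaluated for ADA compared to a stored baseline sample if possible".

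**The concern.** A patient-level classification should give every patient in its scope exactly one label, using one set of samples throughout. Here the positive category uses TE-ADA positive samples, the inconclusive category uses any sample, and the negative category is what is left. Two faults follow: a patient with no detectable antibody can be called inconclusive for neutralizing antibody, and a patient in whom neutralizing antibody was found can have no label.

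Protocol 7.9.2 says that reaction samples are meant to help the sponsor characterize the reaction. Only patients with a reaction sample supply post-baseline data, so any immunogenicity summary will be small, and a few wrong or missing labels would be visible in it.

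**Working it through.** No stated figure depends on these definitions, so there is none to reproduce. The check is to apply the wording to hypothetical patients.

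**Inputs.** Tolerance limits are 480.5 and 1.1 µg/mL (SAP 6.16.1.1). A patient is TE-ADA positive with at least a 4-fold rise over a positive baseline titre, or with a rise to at least 1:10 from a negative baseline (SAP 6.16.1.3). The drug levels (0.5 and 5 µg/mL) and the titres are illustrative. Each patient is assumed to count as evaluable for NAb.

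**Step 1: the gap between the limits.** 480.5 / 1.1 = 436.8, about 437-fold. Any sample with no ADA and with drug above 1.1 and up to 480.5 µg/mL is validly ADA negative, yet its drug level could interfere with the NAb assay.

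**Step 2: classify patients.** The literal reading lets any sample trigger the inconclusive label. The alternative ties all three NAb categories to TE-ADA positive samples.

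| Patient | Literal reading | All tied to TE-ADA positive samples |
|---|---|---|
| A. ADA negative throughout, drug 5 | NAb-inconclusive | Negative, or not applicable |
| B. ADA negative throughout, drug 0.5 | NAb-negative | Negative, or not applicable |
| C. Baseline 1:20, reaction 1:40 with NAb detected, drug 0.5 | No category | Not NAb-positive |
| D. Baseline 1:20 with NAb detected; reaction 1:160, NAb not detected, drug 5 | No category | NAb-inconclusive |
| E. Baseline negative; reaction 1:160, NAb not detected, drug 5 | NAb-inconclusive | NAb-inconclusive |
| F. Baseline negative; reaction 1:160, NAb detected | NAb-positive | NAb-positive |

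A and B have the same antibody findings and differ only in drug level, yet the literal rule labels them differently. In C the rise is 40/20 = 2-fold, below 4-fold, so the sample is not TE-ADA positive and the patient is not NAb-positive. Because a NAb positive sample exists, the patient is not inconclusive and, read literally, not negative. In D the rise is 160/20 = 8-fold, so the reaction sample is TE-ADA positive, but NAb was found only at baseline; the same exclusion leaves no category.

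Limiting the inconclusive trigger to ADA-positive samples would correct A but not C or D.

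**Step 3: compare with the TE-ADA categories.** In the same section, TE-ADA positive, inconclusive and negative all refer to TE-ADA status. The inconclusive wording is nearly the same as for NAb. It causes no difficulty there, because the ADA assay applies to every analysed sample. It does for NAb, because only ADA-positive samples reach that assay.

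**Step 4: titre.** Titre categories carry a last-observation label, but SAP 6.3 has no such rule for titres. Low is below 1:160 and High is 1:1280 or more. Titres of 1:1280 then 1:80 give Low by the last value and High by the maximum. A single sample at 1:1280 is High either way.

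**The case against.** The strongest reply is that patient A is an artefact of reading one sentence alone. The lead-in sentence and Protocol 9.4.2 confine NAb testing to ADA-positive samples. SAP 6.16.1.1 calls a sample inconclusive when an assay finds nothing but drug may have masked a positive, which presupposes that the assay was run. On that view an ADA-negative patient lies outside the NAb categories. The flow chart in Figure RHCR.6.4, which was not available to this review, may say so. That may well be the intent. But the patient-level rule is triggered by a drug level, not by a NAb result, and nothing in the text places ADA-negative patients outside it. The written definition should not depend on inference.

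Second, drug concentration is measured only if needed (Protocol 9.4.2.1, SAP 6.13), so the trigger may seldom be known. This limits how often patient A arises. It does not remove the problem, because SAP 6.16.1.1 needs the drug level to call any sample negative.

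Third, leaving pre-existing NAb out of a treatment-emergent category can be deliberate. That is fair, and C and D need not be NAb-positive. Deliberate exclusion still does not explain why they get no label.

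Fourth, SAP 6.16 specifies no NAb table, and TE-ADA incidence is the only immunogenicity rate that it defines. This stands, and it keeps the point small.

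**Conclusion.** The definitions are wrong as written on two counts: a drug level alone can make a validly ADA-negative patient NAb-inconclusive, and a patient with NAb detected only in a sample that is not TE-ADA positive has no category. The consequence is minor. The data are descriptive and event-driven, and efficacy, alpha and power are unaffected.

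The number of patients cannot be computed. The documents give no ixekizumab concentrations, so the first fault may touch none or all of the sampled ADA-negative patients. They give no reaction rate either. If 1% to 5% of the 480 ixekizumab patients had a reaction sample (an assumption), that would be 0.01 × 480 = 4.8 to 0.05 × 480 = 24, or about 5 to 24 patients with post-baseline data.

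A reader might infer four stronger things that the documents do not support:

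- **That no NAb category is tied to TE-ADA samples.** NAb-positive is expressly tied to them. The fault is that the other two do not match it.
- **That detected NAb is reported as negative or hidden.** The negative definition, read literally, excludes anyone with a NAb positive sample, and the sample-level NAb result remains defined. The patient is unclassified.
- **That nearly every reaction sample would trigger the inconclusive label.** An 80 mg dose falls to 1.1 µg/mL only when diluted into 80 / 1.1 = 72.7 L. Turning that into a share of samples needs a distribution volume, absorption and elimination, none of which the documents give.
- **That a later sample overwrites the titre at the reaction.** This needs a second positive post-baseline sample, which is not scheduled, and one last-value category per patient. The SAP does not say whether titres are categorized per sample or per patient, and a negative sample reports no titre to carry forward.

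**What to change.** In SAP 6.16.1.3, define NAb status only within TE-ADA positive patients and only on their TE-ADA positive samples:

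- **Positive:** NAb detected in at least 1 such sample.
- **Inconclusive:** NAb detected in none, and drug above 1.1 µg/mL in at least 1.
- **Negative:** NAb detected in none, and drug at or below 1.1 µg/mL in all.

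Report other patients under their TE-ADA status, without a NAb label. Show NAb detected in samples that are not TE-ADA positive, including baseline samples, on a separate line.

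As a minor clarification, state which titre (reaction, highest or last) sets the category when a patient has more than one positive post-baseline sample. This changes nothing for a patient with a single reaction sample.

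The cost is a few lines of SAP text. No new samples are needed. The drug level that separates inconclusive from negative is one that the present sample definitions already require.

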6.17. Subgroup Analyses

6.17.1. Efficacy Subgroup Analyses

Subgroup analysis will be conducted on the following efficacy assessments:

- PASI 75, 90, 100 at Week 12 on ITT Population
- sPGA (0, 1) and sPGA (0) at Week 12 on ITT Population

A logistic regression model with treatment, subgroup, and the interaction of subgroup-by-treatment included as factors will be used. The subgroup-by-treatment interaction will be tested at the significance level of 0.10. Treatment group differences will be evaluated within each category of the subgroup using Fisher's exact test, regardless of whether the interaction is statistically significant. Missing data will be imputed using NRI. The treatment differences with 95% CIs by each subgroup category will be reported. If any group within the subgroup is <10% of the total ITT population, only summaries of the efficacy data will be provided (that is, no inferential testing).

The subgroups to be analyzed are listed in [Table RHCR.6.3](#). Additional subgroup analyses on efficacy may be performed as deemed appropriate and necessary.

6.17.2. Safety Subgroup Analyses

Subgroup analyses on safety may be performed as deemed appropriate and necessary.

6.18. Interim Analyses

The study will have one interim database lock once all patients complete Visit 9 (Week 12) or discontinue in the Induction Dosing Period. The interim analysis will include all data collected by the cutoff date, including the data from the Extension Period and the Post Treatment Follow-Up Period. The interim database lock at Week 12 will be considered the primary database lock because all primary and major secondary objectives, except for PASI 100 at Week 24, will be assessed at this time.

Prior to the Week 12 database lock, all members of the study team will be blinded to the treatment allocations. At the time of the Week 12 database lock, study team members that have direct access to study sites and data collection will remain blinded to the treatment allocations until all patients have completed the study (or discontinued on or prior to Week 24) and final database lock has occurred. Site staff, clinical monitors, and patients will remain blinded to the patient treatment allocation until the final Clinical Study Report (CSR) has been approved.

A final database lock will occur after the Post-Treatment Follow-Up Period is completed.

6.19. Clinical Trial Registry Analyses

Additional analyses will be performed for the purpose of fulfilling the Clinical Trial Registry (CTR) requirements.

Analyses provided for the CTR requirements include summary of adverse events, provided as a dataset which will be converted to an XML file. Both Serious Adverse Events and "Other" Adverse Events are summarized: by dosing regimen, by MedDRA preferred term.

- An adverse event is considered "Serious" whether or not it is a treatment emergent adverse event (TEAE).
- An adverse event is considered in the "Other" category if it is both a TEAE and is not serious. For each Serious AE and "Other" AE, for each term and treatment group, the following are provided:

- the number of participants at risk of an event
- the number of participants who experienced each event term
- the number of events experienced.
- Consistent with www.ClinicalTrials.gov requirements, “Other” AEs that occur in fewer than 5% of patients/subjects in every treatment group may not be included if a 5% threshold is chosen (5% is the minimum threshold).
- AE reporting is consistent with other document disclosures such as the CSR.

7. Unblinding Plan

Refer to a separate blinding and unblinding plan.

8. References

- [EMA] European Medicines Agency. Committee for Medicinal Products for Human Use (CHMP). Guideline on clinical investigation of medicinal products indicated for the treatment of psoriasis. November 2004. Available at: http://www.ema.europa.eu/docs/en_GB/document_library/Scientific_guideline/2009/09/WC500003329.pdf. Accessed March 17, 2015.
